Title: attending physician

Address: [name]
Shanghai postal code: 200040

[contact]

mobile [contact]

email [contact]

一、 Programme summary

Protocol name	The efficacy and safety of metformin intervention in elderly overweight or obesity with mild cognitive impairment
Version number/ Version date	V1.0 7 August, 2025
Research objects	Elderly overweight or obesity patients with mild cognitive impairment
Research purposes	To explore the efficacy and safety of metformin in sufficient amount in elderly overweight or obese patients with MCI. To provide reliable evidence for the elderly overweight or obese patients with MCI to delay and reverse the cognitive dysfunction.
Research design	This study was a prospective, randomized controlled, single-center clinical cohort study. Elderly subjects who were overweight or obese with MCI and met the inclusion criteria and did not meet the exclusion criteria were included in this study with informed consent. The subjects were randomly divided into two groups using random number method. In the first group, subjects received metformin sustained-release tablets (1500mg once a day or reduced to the maximum tolerated dose if intolerable) and lifestyle intervention guidance. Subjects in the second group received only lifestyle intervention guidance. All subjects were followed for a period of 26 weeks. History collection, body measurement index evaluation, glycolipid metabolism biochemical test, medication record, and MoCA scale evaluation were conducted during the enrollment phase and the end of follow-up. The insulin sensitivity in central nervous system of subjects in the two groups before and after treatment was evaluated by nasal insulin inhalation combined with fMRI.
Inclusion/ exclusion	Inclusion criteria

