criteria	
A. age: 60 -75 years;
 
B. Body mass index: $\geq 24 \text{kg/m}^2$;
 
C. glycated hemoglobin $< 8.5\%$;
 
D. The scores of the MoCA scale are 20–26 (education > 10 years) or 20–25 (education ≤ 10 years);
 
E. sign informed consent forms;
 
Exclusion criteria
 
A. Anyone who takes any hypoglycemic drug within 8 weeks prior to enrollment;
 
B. type 1 diabetes;
 
C. Central nervous system magnetic resonance imaging cannot be completed;
 
D. A history of alcohol or drug addiction;
 
E. Severe gastrointestinal diseases, history of gastrointestinal surgery, severe cardiopulmonary dysfunction, malignant tumor and other diseases;
 
F. Abnormal liver function (liver enzyme index is more than 2.5 times the upper limit of the reference range) or renal function (estimated glomerular filtration rate $< 45 \text{ mL/min}$);
 
G. There were relevant situations that the investigator judged were not suitable for inclusion in the study.

Study drug	
Drug name: metformin hydrochloride sustained-release tablets (Gehuazhi)
 
Drug specification: 500mg

Sample size	
The change in blood flow volume of cerebral regions shown by fMRI after nasal insulin inhalation was used as the research endpoint. According to the results of previous literature, the difference between groups after drug intervention was 20%, and the standard deviation was 20%. When the accuracy was 0.05 and the test efficiency $1-\beta$ was 0.8, the required sample size for each group was obtained from the sample size calculation formula: $n_1=n_2=23$. Considering the existence of a certain shedding ratio, and calculated based on the shedding rate of 15%, 54 patients, 27 in each group, were to be included in the study.

Statistical method	
SPSS 22.0 statistical analysis software was used for calculation. All statistical tests were performed using a two-sided test, and $P \leq 0.05$ was considered statistically significant for the difference tested. Enumeration data were described by constituent ratio, and measurement data were described by mean, standard deviation, median, and interquartile. Statistical analysis: Appropriate methods were used for analysis according to the types of indicators. T test or Wilcoxon rank sum test was used for inter-group comparison of quantitative data, and chi-square test was used for classified data.

---------------------------	--

二、Contents

二、	Programme summary	4

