- B. Body mass index: $\geq 24\text{kg}/\text{m}^2$;
- C. glycated hemoglobin $< 8.5\%$;
- D. The scores of the MoCA scale are 20–26 (education > 10 years) or 20–25 (education ≤ 10 years);
- E. sign informed consent forms;

2. Exclusion criteria

- A. Anyone who takes any hypoglycemic drug within 8 weeks prior to enrollment;
- B. type 1 diabetes;
- C. Central nervous system magnetic resonance imaging cannot be completed;
- D. A history of alcohol or drug addiction;
- E. Severe gastrointestinal diseases, history of gastrointestinal surgery, severe cardiopulmonary dysfunction, malignant tumor and other diseases;
- F. Abnormal liver function (liver enzyme index is more than 2.5 times the upper limit of the reference range) or renal function (estimated glomerular filtration rate $< 45\text{ mL/min}$);
- G. There were relevant situations that the investigator judged were not suitable for inclusion in the study.

3. Exit criteria

All subjects had the right to withdraw from the study at any stage of the study and the investigator had the right to discontinue observation of subjects who:

- 1) Continuing to participate in the seminar would cause unnecessary damages to the subjects;
- 2) The subjects had poor compliance and did not cooperate with the researchers in

relevant examinations and interventions;

- 3) Subjects who were found not to meet the inclusion criteria after participating in the study;
- 4) Subjects who were found to meet the exclusion criteria after participation in the study.

九、 Sample size assessment

The change in blood flow volume of cerebral regions shown by fMRI after nasal insulin inhalation was used as the research endpoint. According to the results of previous literature, the difference between groups after drug intervention was 20%, and the standard deviation was 20%. When the accuracy was 0.05 and the test efficiency $1-\beta$ was 0.8, the required sample size for each group was obtained from the sample size calculation formula: $n_1=n_2=23$. Considering the existence of a certain shedding ratio, and calculated based on the shedding rate of 15%, 54 patients, 27 in each group, were to be included in the study.

十、 Study Endpoints

1. Effectiveness

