at any dose or at any time during observation. Adverse events are classified as serious adverse events if one or more of the following criteria are met: 1. Death 2. Life-threatening (meaning that the patient in whom the event occurred was at risk of dying immediately at the time of the event; Does not include those events which, if more serious, could result in the death of the patient) 3. Lead to hospitalization or prolonged hospitalization 4. Lead to permanent or significant loss of labor or disability 5. Congenital malformations. Medical events that have not yet resulted in death, life risk, or hospitalization that, after appropriate medical judgment, may be hazardous to the patient or subject or require medical or surgical treatment to avoid such occurrences should also be considered SAE.

If any adverse event occurs, the patient should report it to the researcher in time. The researcher should make a detailed record at the corresponding position on the case report form. The researcher should assist the patient to actively handle the adverse event and strive for the best prognosis while respecting the patient's will and choice. Meanwhile, possible adverse events are prevented and treated. As metformin was used in this study, it was expected that possible adverse events in this study would include: gastrointestinal reaction conditions, such as abdominal pain, diarrhea, and abdominal distension. In the case of serious adverse events, the Ethics Committee and relevant health authorities will be reported within 24 hours and the subject will be treated promptly.

十三、 Statistical Analysis Plan

SPSS 22.0 statistical analysis software was used for calculation. All statistical tests were performed using a two-sided test, and $P \leq 0.05$ was considered statistically significant for the difference tested. Enumeration data were described by constituent ratio, and measurement data were described by mean, standard deviation, median, and interquartile. Statistical analysis: Appropriate methods were used for analysis according to the types of indicators. T test or Wilcoxon rank sum test was used for inter-group comparison of quantitative data, and chi-square test was used for classified data.

十四、 Testing-related Ethics

1. compliance with the requirements of the declaration of helsinki and laws and regulations

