After all the study data were entered and locked, the database was submitted to the statistical analyst for statistical analysis according to the requirements of the statistical plan. After the statistical analysis was completed, the general and sub-reports for statistical analysis were written by the statistical analysts and submitted to the principal investigator of the trial for writing the study report.

5) Data confidentiality

All subject information used in this study must be kept strictly confidential, and information about subjects who participated in the study and who were enrolled in the study must be kept confidential. Subject information and study data will be identified by study number. Information that identifies him or her will not be disclosed to members outside the study group unless subject approval is obtained. Subject identity was to be kept confidential by all study members. The subject's profile will be

maintained in a locked cabinet for access by the investigator only. To ensure that the study was conducted as required, members of the ethics committee were provided with access to subject profiles at the study unit as necessary. No personal information will be disclosed for the subject when the results of this study are published.

All study members should keep the study data confidential. They should not inform the members other than the research group of the study data without the permission of the main investigator, and should not transfer the study data to external units without the permission of the hospital.

6) Quality control

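### The protocol fixes an unadjusted t or Wilcoxon test for outcomes measured at both V0 and V7 and does not say whether V7 values or changes are compared; adjusting for V0 would use data already collected

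*Protocol*

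**What the plan says.** Section 十三, which is itself titled Statistical Analysis Plan, states: "T test or Wilcoxon rank sum test was used for inter-group comparison of quantitative data", with a chi-square test for categorical data. The synopsis repeats this. The preceding sentence, "Appropriate methods were used for analysis according to the types of indicators", names no model. No covariate appears anywhere in the analysis text.

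Section 十一 schedules nasal insulin with fMRI, and MoCA, at V0 and again at V7 (26 weeks). The appendix likewise places MoCA at V0 and V7.

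On which quantity enters the test, the protocol gives only these indications:

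- Synopsis, research design: central insulin sensitivity of "subjects in the two groups before and after treatment was evaluated by nasal insulin inhalation combined with fMRI".
- Section 九: "The change in blood flow volume of cerebral regions shown by fMRI after nasal insulin inhalation was used as the research endpoint". Here the change is the blood-flow response to insulin within a scanning session, not a difference between visits.
- Section 九, planning assumption: "the difference between groups after drug intervention was 20%, and the standard deviation was 20" (per cent). It does not say whether this SD is that of a V7 response or of its change from V0.
- Section 十: MoCA is named as a score, with no visit or change attached.

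**The concern.** A test of V7 values alone discards the V0 measurement. A test of changes subtracts it in full, that is, with a fixed weight of 1. Which of the two loses power depends on the V0–V7 correlation and on the ratio of the two SDs, neither of which is known yet. A linear model with V0 as a covariate estimates the weight from the data and stays close to the better of the two.

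The trial is small (54 randomised, 23 per arm expected to complete), and it is not sized for MoCA. Precision matters most for MoCA and for an fMRI effect smaller than the one planned. Leaving the input open also leaves two possible primary results where there should be one.

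**Working it through.** **Inputs from the protocol.** Difference 20%, SD 20% (standardised effect 1.0); two-sided 0.05; power 80%; 23 per arm, raised to 27 for 15% dropout.

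**The protocol's own figure.** With these inputs the normal approximation gives 16 per arm and the t test 17. The stated 23 corresponds to a two-sided t test at 90% power (22.02, rounded up). That mismatch is a separate matter; 23 per arm is used below as stated.

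**Assumed inputs (not in the protocol).** V0–V7 correlation rho = 0.3/0.5/0.7; ratio k = SD(V0)/SD(V7); and, for illustration, a smaller effect of d = 0.5 SD.

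**Method.** Noncentral t with 23 per arm, 44 degrees of freedom unadjusted and 43 adjusted. Variance relative to the V7-only comparison:

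- change: 1 + k² − 2·rho·k
- adjusted: (1 − rho²)(1 + F/44), averaged over F(1,44) to allow for chance V0 imbalance (mean factor 1 + 1/42)

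Example with rho = 0.5, k = 1: change 1 + 1 − 1 = 1.00, the same as V7-only; adjusted 0.75 × (1 + 1/42) = 0.77.

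**1. Effect of 0.5 SD**

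| Analysis | rho 0.3 | rho 0.5 | rho 0.7 |
|---|---|---|---|
| V7 only | 38.2% | 38.2% | 38.2% |
| Change, k = 1 | 28.9% | 38.2% | 57.2% |
| Change, k = 0.6 | 38.2% | 47.7% | 63.3% |
| Adjusted for V0 | 40.5% | 47.3% | 63.1% |

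A V7-only test would need about 25/30/44 per arm to match the adjusted power.

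The k = 0.6 row is relevant to MoCA because entry is restricted ("The scores of the MoCA scale are 20–26", or up to 25 with 10 years of education or less), which narrows the V0 distribution. In that case adjustment gains about 2 points over the change at rho 0.3 and nothing at 0.5 or 0.7. Over V7-only it gains 2/9/25 points.

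**2. If 0.3/0.5/0.7 are correlations before entry restriction.** With V0 SD cut to u = 0.6 of its unrestricted value, rho′ = rho·u/√(1 − rho² + rho²u²) = 0.19/0.33/0.51. Power at 0.5 SD: adjusted 38.5/41.1/47.7%, V7-only 38.2%, change 33.9/38.2/46.3%.

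**3. The protocol's own effect, equal SDs**

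| 20% SD belongs to | Analysis | rho 0.3 | rho 0.5 | rho 0.7 |
|---|---|---|---|---|
| V7 value | V7 only | 91.2% | 91.2% | 91.2% |
| V7 value | Change | 80.0% | 91.2% | 99.0% |
| V7 value | Adjusted | 93.0% | 96.6% | 99.6% |
| Change | V7 only | 97.5% | 91.2% | 72.9% |
| Change | Change | 91.2% | 91.2% | 91.2% |
| Change | Adjusted | 98.2% | 96.6% | 94.4% |

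In the lower half, the effect in V7 SD units is √(2 − 2·rho) = 1.18/1.00/0.77.

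**4. Downside of adjusting.** At rho = 0 and 0.5 SD, adjusted power is 37.4% against 38.2% for V7-only, a loss of 0.7 points before rounding. The two cross at |rho| of about 0.15. The largest loss at any effect size is about 1 point (near 0.75 SD). Against a change score the largest loss, when rho equals k, is also about 1 point.

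**5. Type I error.** In simulation (40,000 trials per setting) each single test holds 4.7–5.1%. If either the V7 or the change test could be reported as positive, the rate would be 8.7/9.0/9.4% at k = 1 and 7.6/7.4/7.8% at k = 0.6.

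**The case against.** The strongest reply is that nothing here is an error: a two-sample test of a randomised comparison is a legitimate primary analysis. That stands, and it limits the point to precision.

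Second, covariates and the choice between V7 and change are often left to a separate plan. Section 十九 says "the database was submitted to the statistical analyst for statistical analysis according to the requirements of the statistical plan". This weakens the point without removing it: the protocol's own section carries the title of that plan and names unadjusted tests, so a separate document using an adjusted model would depart from it.

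Third, the passages do not flatly contradict one another. The synopsis sentence may describe only when measurements are taken, and section 九 reads most naturally as a comparison after treatment. That is fair; the input is under-specified, not contradictory.

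Fourth, the larger gains rest on a correlation and a 0.5 SD effect that the protocol does not give. The fMRI measure is itself a within-session response, so its V0–V7 correlation could be low. At rho 0.2 adjusted power is 38.7% against 38.2%; at 0.1 it is 37.7%, slightly worse. At the planned effect only one combination in the table falls below 80%. All of this stands, but the possible loss is about 1 point while the possible gain is much larger.

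Fifth, no passage proposes choosing the test after seeing the results, so the 8–9% error rate shows why the input should be stated and is not a charge against the plan. Finally, a linear model for a bounded 30-point score in about 23 patients per arm invites a check on residuals, which is a reason to keep the rank test as a sensitivity analysis.

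**Conclusion.** The point holds as a worthwhile improvement in precision, not as a validity failure. The protocol commits to an unadjusted test for outcomes whose baseline values it already collects, and it leaves the input to that test open.

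The size depends on the unknown correlation: from about nothing below 0.2 to 25 points of power over a V7-only test at 0.7 (0.5 SD effect). For MoCA with restricted entry, the gain over a change score is negligible if its V0 SD is about 0.6 of its V7 SD. At the planned effect, adjustment protects against picking the weaker unadjusted contrast, where power could be 80% or 73%.

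These figures assume 23 completers per arm and correlations of 0.3 to 0.7; those at the planned effect also assume equal V0 and V7 SDs. Confidence is medium because the correlation is assumed.

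**What to change.** In section 十三 and the synopsis, make the primary analysis of each of the two outcomes a linear model of the V7 value on group and the V0 value. For fMRI the V7 value is the blood-flow response to nasal insulin at that visit. Keep the t or Wilcoxon test as a sensitivity analysis and state in advance whether its input is the V7 value or the change.

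In section 九, state which variable the 20% SD describes. When the fMRI outcome is written into the model, name the brain region and response measure as well, since no choice of test settles that.

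The cost is one paragraph, repeated in the synopsis, agreed before the analysis period that section 十六 sets for April to September 2026. SPSS, already named, fits the model. No new visits, measurements or participants are needed, and the statistical cost is at most about 1 point of power.

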			2 ND TRI-												
ATTENTION		Read list of digits (1 digit/ sec).	Subject has to repeat them in the forward order. [] 2 1 8 5 4 Subject has to repeat them in the backward order. [] 7 4 2						___/2						
Read out the following numbers. Each time the number is 1, the patient knocks 1 on the table. No score is given if the error number is greater than or equal to 2. [] 52139411806215194511141905112									___/1						
Serial 7 subtraction starting at 100. [] 93 [] 86 [] 79 [] 72 [] 65 4 or 5 correct subtractions: 3 pts, 2 or 3 correct: 2 pts, 0 or 1 correct: 0									___/3						
LANGUAGE		Repeat: I only know that Zhangliang is the one to help today. [] The cat always hid under the couch when dogs were in the room. []							___/2						
Fluency: Name maximum number of animal names in one minute. [] _____ (N≥11 words)									___/1						
ABSTRACTION		Similarity between e.g. banana - orange = fruit [] train - bicycle [] watch - ruler							___/2						
DELAYED RECALL	Has to recall words WITH NO CUE	[]	FACE []	VELVET []	CHURCH []	DAISY []	RED []	Points for UNCUED recall only	___/5						
	Category cue														
	Multiple choice cue														
ORIENTATION		[] Date [] Month [] Year [] Day [] Place [] City							___/6						
TOTAL [] /30
